#### 6.3.19 Remote Contact Reminder for Week 16 Visit

Participants will be contacted 2 weeks prior to the week 16 visit via the locator information provided and reminded that they are due for their SVR assessment. If the participant cannot be reached after 3 attempts, the secondary contact will be contacted. This information is not recorded on the eCRF.

#### 6.3.20 Evaluation of Step 2 Entry Requirements

[Sections 4.3](#) and [4.4](#) specify requirements for Step 2 entry. Recurrence and virologic failure should be documented. Determination of suspected relapse versus reinfection versus undefined post-treatment viremia by communication with the designated team member should be documented. These should be recorded on the eCRF.

The informed consent form for Step 2 must be reviewed and signed by the participant prior to Step 2 entry.

### 7.0 ADVERSE EVENTS AND STUDY MONITORING

#### 7.1 Definition of AEs

An AE is any unfavorable and unintended sign (including an abnormal laboratory finding), symptom, or diagnosis that occurs in a study participant during the conduct of the study REGARDLESS of the attribution (i.e., relationship of event to medical

treatment/study product/device or procedure/intervention). This includes any occurrence that is new in onset or aggravated in severity or frequency from the baseline condition.

## 7.2 AE Collection Requirements for This Protocol

From study enrollment, all AEs must be recorded on the eCRFs if any of the following criteria have been met:

- All Grade  $\geq 2$  AEs
- All AEs that led to a change in study treatment/intervention regardless of grade or attribution.
- All AEs meeting SAE definition or EAE reporting requirement

NOTE: SAEs or events meeting EAE reporting requirements should also be entered into the DAIDS Adverse Experience Reporting System (DAERS), an Internet-based reporting system.

All AEs that are reported must have their severity graded. To grade AEs, sites must refer to the Division of AIDS Table for Grading the Severity of Adult and Pediatric Adverse Events (DAIDS AE Grading Table), corrected Version 2.1, July 2017, which can be found on the DAIDS RSC website at <https://rsc.niaid.nih.gov/clinical-research-sites/daids-adverse-event-grading-tables>.

### Serious Adverse Events (SAEs)

An SAE is defined as any untoward medical occurrence that:

- Results in death
- Is life-threatening
- Requires inpatient hospitalization or prolongation of existing hospitalization
- Results in persistent or significant disability/incapacity
- Is a congenital anomaly/birth defect
- Is an important medical event that may not be immediately life-threatening or result in death or hospitalization but may jeopardize the patient or may require intervention to prevent one of the other outcomes listed in the definition above).

## 7.3 Expedited Adverse Event (EAE) Reporting to DAIDS

### 7.3.1 Expedited Reporting of Adverse Events to DAIDS

Requirements, definitions and methods for expedited reporting of AEs are outlined in Version 2.0 of the DAIDS EAE Manual, which is available on the RSC website at <https://rsc.niaid.nih.gov/clinical-research-sites/manual-expedited-reporting-adverse-events-dais>.

The DAIDS Adverse Experience Reporting System (DAERS), an internet-based reporting system, must be used for EAE reporting to DAIDS. In the event of system outages or technical difficulties, EAEs may be submitted using the DAIDS

EAE Form. This form is available on the DAIDS RSC website at <https://rsc.niaid.nih.gov/clinical-research-sites/paper-eae-reporting>.

For questions about DAERS, please contact NIAID CRMS Support at [[contact]](mailto:[contact]). Please note that site queries may also be sent from within the DAERS application itself.

For questions about expedited reporting, please contact the DAIDS RSC Safety Office at ([[contact]](mailto:[contact])).

### 7.3.2 Reporting Requirements for this Study

- The SAE Reporting Category, as defined in Version 2.0 of the DAIDS EAE Manual, will be used for this study.
- The study agents for which expedited reporting are required are: glecaprevir/pibrentasvir (G/P) FDC and ribavirin (RBV)
- Though not an AE, the study investigator must report to the sponsor or designee, within 3 business days of identification, any pregnancy occurring in a female participant or a female partner of a male participant, during the study or within 24 weeks of the last dose of RBV. Any complication of pregnancy affecting a female participant or female partner of a male participant, and/or fetus, and/or newborn that meets SAE criteria must be reported as an SAE. See [section 8.2](#) for pregnancy reporting requirements.

### 7.3.3 Grading Severity of Events

The Division of AIDS Table for Grading the Severity of Adult and Pediatric Adverse Events (DAIDS AE Grading Table), corrected Version 2.1, July 2017, must be used and is available on the DAIDS RSC website at <https://rsc.niaid.nih.gov/clinical-research-sites/daids-adverse-event-grading-tables>.

### 7.3.4 Expedited AE Reporting Period

- The expedited AE reporting period for this study is week 0 to week 28 for all participants except those who proceed to Step 2. For individuals who proceed to Step 2, the reporting period would be dependent on the length of their Step 2 regimen. Each Step 2 participant will have expedited AE reporting up to 12 weeks after their last dose of study drug except for RBV for which expedited AE reporting would continue till week 24 after last medication dose. For Step 2 of this study expedited AEs would only be collected on Step 2 participants who are on study drugs (G/P) or G/P and RBV.

- After the protocol-defined AE reporting period, unless otherwise noted, only suspected, *unexpected* serious adverse reactions (SUSARs), as defined in Version 2.0 of the EAE Manual, will be reported to DAIDS if the study staff become aware of the events on a passive basis (from publicly available information).

#### 7.4 Study Monitoring

A5380 core team members (including study chairs, medical officer, and statisticians) will monitor the conduct and safety of the study via regular summaries of accrual, AEs, study conduct (including premature study discontinuations and premature study treatment discontinuations), data completeness, and specimen collection, as appropriate. The core team will review the individual participant-level HCV virology data as outlined in [section 10.5](#).

The DAIDS clinical representative will review and assess select EAE reports for potential impact on the study participant safety and protocol conduct as per DAIDS policies, guidance documents, and standard operating procedures (SOPs), as applicable. Additionally, the DAIDS clinical representative will review aggregated AE summaries prepared every 3 months by the Statistical and Data Analysis Center (SDAC).

The study will undergo interim review at least annually by an ACTG-appointed Study Monitoring Committee (SMC). The first planned interim review will occur when the study week 8 data are available from the first 10 participants or one year after the enrollment of the first study participant, whichever occurs first. An interim review may also be convened if a concern is identified by the DAIDS clinical representative, the study chairs, or study statistician in consultation with the team. See [section 10.5](#) for statistical and other considerations related to interim monitoring.

Detailed plans for study monitoring will be outlined in a Study Progress, Data, and Safety Monitoring Plan (SPDSMP) developed by the Statistical and Data Management Center (SDMC) prior to enrollment of the first participant.

### 8.0 CLINICAL MANAGEMENT ISSUES

#### 8.1 Toxicity

It is possible that some participants will experience transient or prolonged AEs during the trial. To minimize the effects of these dosing modifications on the eventual evaluation of the safety, tolerability, and activity of study treatment, the principles in the following sections will be used to determine the appropriate dose adjustment.

Grades 1 and 2 AEs associated with G/P or RBV require no change in study treatment but close follow-up; with the exception that modifications of RBV dosing for Grades 1 and 2 anemia are provided in [section 8.1.2](#).

### 8.1.1 Management of Side Effects of G/P

Most AEs are expected to be mild in severity. However, if a SAE occurs, administration of G/P may be discontinued due to clinical or laboratory events. For participants also on a ritonavir (RTV)-boosted HIV PI or a cobicistat-containing regimen there is potential for higher exposures.

Dose reduction of G/P will not be allowed in the study. If G/P is stopped for toxicity, it will not be restarted.

All participants must complete weeks 8, 12, 16, and 28 visits (Step 1) or one of the following visits in Step 2 depending on re-treatment duration: week R+20, R+24, or R+28, R+32, R+36, and R+40 visits.

Participants who meet any of the following laboratory criteria should stop treatment with G/P:

- Confirmed elevation of ALT and/or AST  $>3 \times$  values measured upon study entry
- Confirmed direct bilirubin  $>2 \times$  values measured upon study entry
- Any  $\geq$ Grade 3 rash associated with constitutional symptoms
- Any Grade 4 event assessed as related to treatment with G/P

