**Risks of Study Drugs**

The drugs used in this study may have side effects, such as headaches, fatigue, diarrhea, nausea, asthenia, pruritic skin, and abnormal liver function tests. There is a risk of serious and/or life-threatening side effects when certain non-study medications are taken with the study drugs.

Drug interactions may increase the chances of side effects, may affect the levels of ARVs or other medications and/or cause changes in liver enzymes and other abnormal blood tests. Certain HIV medications may be changed to reduce this risk. For certain HMG-CoA reductase inhibitors (statins), others may require dose adjustment or careful monitoring. For digoxin, the dose should be reduced and closely monitored while on G/P. Drug interactions that lower the levels of glecaprevir or pibrentasvir may decrease the participant's chances for a cure of hepatitis C and/or select for drug resistance. Certain drugs known to cause lower levels of glecaprevir or pibrentasvir will be avoided.

Some people with HCV and HBV coinfection receiving DAA therapy for HCV, have experienced reactivation of HBV. Some of these cases have led to severe hepatitis, liver failure and death. This has been reported mostly in individuals who are positive for HBsAg and extremely rarely in those who appear to have resolved HBV infection by lab tests. Those with HBsAg will be excluded, while those with resolved HBV infection will be monitored.

Ribavirin may be used in Step 2 for those with detection of viremia after 4 weeks of glecaprevir/pibrentasvir in Step 1. The most common AE of RBV therapy is anemia due to hemolysis. Anemia typically occurs within 1 to 2 weeks of initiating RBV therapy and usually resolves within 4 to 8 weeks of drug discontinuation or dose reduction. Indirect bilirubin elevation is commonly seen in those participants with anemia secondary to RBV-induced hemolysis.

Another major side effect of RBV is its teratogenicity. It is therefore strongly recommended that pregnant women or breastfeeding women and men with pregnant sexual partners not receive RBV. Women who become pregnant on study and men on study whose partners become pregnant must discontinue study treatment and complete the discontinuation evaluations as indicated in [section 8.2](#).

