## 6.0 CLINICAL AND LABORATORY EVALUATIONS

## 6.1 Schedule of Evaluations (SOE)

Table 6.1-1: SOE: Step 1 - Study Visits for 4-week Treatment and Post-Treatment Follow-up

Evaluation	Screening	Entry (Day 0)	On Treatment		Treatment Completion	Post-treatment					HCV Recurrence/ Virologic Failure Confirmation (see Event-Driven Evaluations in section 6.2.4 )	HIV-1 Virologic Breakthrough Confirmation( see Event-Driven Evaluations in section 6.2.4 )	Premature Study and /or Treatment Discontinuation Evaluations				
			Weeks; See section 6.2.3 for study windows														
			1	2		4	8	12	14	16/SVR12	28						
Documentation of HIV-1 (if applicable)	X																
Documentation of Acute HCV Infection	X																
Documentation of Cirrhosis Status	X																
Documentation of Historical Labs (see section 6.3.4 )	X																
Medical History	X																
Medication History	X	X															
Clinical Assessments (see section 6.3.7 )	X	X	X	X	X	X	X	X	X	X	X	X	X	X			
Hematology	X	X									X						
Chemistries	X	X	X	X	X	X	X	X	X	X	X			X			

Evaluation	Screening	Entry (Day 0)	On Treatment		Treatment Completion	Post-treatment					HCV Recurrence/ Virologic Failure Confirmation (see Event-Driven Evaluations in section 6.2.4 )	HIV-1 Virologic Breakthrough Confirmation (see Event-Driven Evaluations in section 6.2.4 )	Premature Study and /or Treatment Discontinuation Evaluations	
			1	2		4	8	12	14	16/SVR12	28			
			Weeks; See section 6.2.3 for study windows											
Liver Function Tests (LFTs)	X	X	X	X	X	X	X	X		X	X	X		X
Calculated CrCl	X	X			X					X	X	X		X
Coagulation Markers	X	X		X	X	X				X		X		X
Urine Sample for Substance Use Screen		X	X	X	X	X	X	X		X	X	X		X
FSH	X													
Pregnancy Testing	X	X	X	X	X	X	X			X	X	X		X
Serologies	X					X (see section 6.3.8 )					X			
HCV Antibody	X					X (see section 6.3.8 )								
CD4+/CD8+ (for participants with HIV-1 infection)	X	X			X					X				X
Stored Plasma and PBMC for Immunologic Studies	X	X			X		X			X	X	X		X
Plasma HCV RNA (screening performed at local lab, see section 6.3.10 )	X													
Plasma HCV RNA (real-time, see section 6.3.10 )		X	X	X	X	X	X	X		X	X	X		X

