Evaluation	Re-Treatment Entry/Initiation	On-Retreatment (Weeks) R = Step 2 Entry ReTx=Retreatment					Post-Retreatment		HCV Recurrence/Virologic Failure (see Event Driven Evaluations in section 6.2.4 ) Confirmation	HIV-1 Virologic Breakthrough Confirmation (see Event-Driven Evaluations in section 6.2.4 )	Premature Study and /or Treatment Discontinuation Evaluations
		R+2 (RBV regime ns only)	R+4	R+8	R+12 (12 & 16 weeks ReTx only)	R+16 (16 weeks ReTx only)	SVR12 visit (R+20, R+24 or R+28, depending on re-treatment duration)	Only for RBV exposed (R+32, R+36 or R+40, depending on re-treatment duration)			
		See section 6.2.3 for study windows									
Evaluation of Step 2 Entry Requirements (see section 6.3.20 )	X										
Clinical Assessments (see section 6.3.7 )	X	X	X	X	X	X	X	X	X		X
Hematology, Chemistries	X	X	X	X	X	X	X		X		X
LFTs (see section 6.3.8 )									X		
Serologies (see section 6.3.8 )	X								X		
Calculated CrCl (if on RBV)	X	X	X	X	X	X					X
Pregnancy Testing (see section 6.3.8 )	X	X	X	X	X	X	X	X			X

Evaluation	Re-Treatment Entry/ Initiation	On-Retreatment (Weeks) R = Step 2 Entry ReTx=Retreatment					Post-Retreatment		HCV Recurrence/Virologic Failure (see Event Driven Evaluations in section 6.2.4 ) Confirmation	HIV-1 Virologic Breakthrough Confirmation (see Event-Driven Evaluations in section 6.2.4 )	Premature Study and /or Treatment Discontinuation Evaluations	
		R+2 (RBV regime ns only)	R+4	R+8	R+12 (12 & 16 weeks ReTx only)	R+16 (16 weeks ReTx only)	SVR12 visit (R+20, R+24 or R+28, depending on re- treatment duration)	Only for RBV exposed (R+32, R+36 or R+40, depending on re- treatment duration)				
See section 6.2.3 for study windows												
CD4+/CD8+ (for participants with HIV-1 infection)	X			X			X	X				X
Stored Plasma and PBMC (see section 6.3.9 )	X		X		X		X	X		X		X
Plasma HCV RNA (real-time, see section 6.3.10 )	X	X	X	X	X	X	X			X		X
Plasma HCV Genotype (see section 6.3.10 )										X		
Plasma HIV-1 RNA (for participants with HIV-1 infection, real-time, see section 6.3.10 )			X	X	X	X	X			X	X	X
Stored Serum for HIV-1/HCV Studies (see section 6.3.10 )		X	X	X	X		X			X	X	X

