#### Chemistries

Creatinine, glucose, lipase, potassium, and sodium.

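### As read, Table 6.1-2 schedules no liver tests from Step 2 entry to the end of re-treatment, so the ALT/AST and direct-bilirubin stopping criteria in Protocol 8.1.1 have no routine data over 56 to 112 days of G/P

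*Protocol*

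**What the plan says.** Protocol 8.1.1 sets the rule for stopping the study drug: "Participants who meet any of the following laboratory criteria should stop treatment with G/P". Four criteria follow:

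- confirmed ALT and/or AST above 3 times the value at study entry;
- confirmed direct bilirubin above 2 times that value;
- a rash of Grade 3 or higher with constitutional symptoms;
- any Grade 4 event judged related to G/P.

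The criteria carry no restriction to Step 1. The same section lists the follow-up visits to be completed for both steps, including "one of the following visits in Step 2 depending on re-treatment duration". It adds: "If G/P is stopped for toxicity, it will not be restarted".

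Table 6.1-2 is the Step 2 schedule. Its row "Hematology, Chemistries" is marked at entry, every on-treatment visit, SVR12, failure confirmation and premature discontinuation. The separate LFT row is marked once, under HCV recurrence/virologic failure confirmation. Protocol 6.3.8 defines chemistries as "Creatinine, glucose, lipase, potassium, and sodium", and puts ALT, AST and direct bilirubin in the LFT panel. Letters of Amendment #1 to #4 and Clarification Memos #1 to #3 add no scheduled on-treatment LFT to Step 2. Table 6.1-1 marks LFTs at Step 1 entry and at weeks 1, 2 and 4.

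**The concern.** Two of the four stopping criteria are laboratory thresholds, and the step with the longer drug exposure schedules no measurement of them. An asymptomatic rise in transaminases or direct bilirubin during re-treatment would come to light only if a site ordered a test on its own judgement, a listed co-medication prompted one, or a failure-confirmation visit took place. The rule would then be applied unevenly between sites and possibly late.

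The protocol's own reasoning points towards monitoring. Section 2.3 names "asthenia, pruritic skin, and abnormal liver function tests" among the possible side effects. Section 2.2 allows boosted darunavir and elvitegravir/cobicistat on two grounds: G/P exposure is only 4 weeks, and participants have no cirrhosis. Section 5.4.1 does not exclude these drugs from Step 2, where only the second ground persists (4.4.1). Section 11.0 notes that they raise glecaprevir exposure, with a theoretical risk to the liver. On HBV reactivation, Section 2.3 says HBsAg-positive people are excluded "while those with resolved HBV infection will be monitored", but no on-treatment test in Step 2 is scheduled for that purpose.

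What is at stake is participant safety in re-treatment. The primary efficacy result is not.

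**Working it through.** **Reading the rows.** On the first page of Table 6.1-2 each row has 11 cells: entry, R+2 (ribavirin regimens only), R+4, R+8, R+12 (12- and 16-week re-treatment), R+16 (16-week only), SVR12, ribavirin follow-up, HCV failure confirmation, HIV breakthrough confirmation, premature discontinuation.

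- Hematology/chemistries: marks in cells 1 to 7, 9 and 11.
- LFTs: one mark, in cell 9.

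**Duration.** Protocol 5.1.3 gives 8 to 16 weeks. In days: 8 × 7 = 56, 12 × 7 = 84, 16 × 7 = 112.

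**Visits from entry to end of treatment, and how many schedule an LFT.**

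| Regimen | Visits | LFTs scheduled | Days of G/P |
|---|---|---|---|
| 2A (8 weeks) | entry, R+4, R+8 | 0 of 3 | 56 |
| 12 weeks without ribavirin (2D at its minimum) | entry, R+4, R+8, R+12 | 0 of 4 | 84 |
| 2C (16 weeks) | entry, R+4, R+8, R+12, R+16 | 0 of 5 | 112 |
| 2B (16 weeks, ribavirin) | entry, R+2, R+4, R+8, R+12, R+16 | 0 of 6 | 112 |
| Step 1 (4 weeks) | entry, weeks 1, 2, 4 | 4 of 4 | 28 |

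The longest nominal on-treatment gap between LFTs in Step 1 is week 2 to week 4, or 14 days.

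**Which reference value.** The liver criteria compare with study entry. The exclusion criteria use that term for Step 1 (4.2) and mostly speak of Step 2 entry for Step 2 (4.4), so the literal reference is Step 1 entry, during acute hepatitis. If ALT at Step 1 entry were 1, 5 or 10 times ULN, the trigger in Step 2 would be above 3 × 1 = 3, 3 × 5 = 15 or 3 × 10 = 30 times ULN. The 5 and 10 are ALT levels that can qualify a participant under 4.1.3; ALT may have fallen by entry, so these are illustrations. The other reading, a Step 2 entry value, has no scheduled measurement behind it.

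**Reach.** Expected non-SVR participants = n × (1 − true SVR12).

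- n = 44: 44 × 0.05 = 2.2 and 44 × 0.20 = 8.8.
- n = 50, the maximum enrollment: 50 × 0.05 = 2.5 and 50 × 0.20 = 10.

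These are expected values, not bounds. Not all would enter Step 2: missing or lost participants count as SVR12 failures (10.1) without entering re-treatment, some may opt out (3.0), and some may take regimens without G/P.

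**The case against.** **The finding rests on blank cells in a table read by machine.** Some extraction faults are visible: several rows in Table 6.1-1, and in the continuation of Table 6.1-2, have one cell more than their headers. The LFT row, however, has the same 11 cells as its neighbours on the first page, and its single mark agrees with 6.2.4, which calls for a hepatic panel at recurrence or failure. A fault is unlikely but should be excluded on the original page. The Manual of Procedures was not available.

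**The rule may be meant for Step 1.** Its reference value points there, and the Step 2 wording in 8.1.1 concerns follow-up visits. Still, nothing restricts the criteria to Step 1, and G/P is given in both steps. The ambiguity is itself a reason to amend the text.

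**Lighter monitoring may be deliberate.** Section 2.1 reports 0.1% permanent discontinuation for adverse reactions over 8 to 16 weeks of G/P, Section 2.2 reports no ALT elevations with darunavir/ritonavir, and known cirrhosis is excluded. This lowers the expected event rate. It does not supply the data the criteria need. Visit examinations, ad hoc tests, the prompts in Tables 5.4.2-1 and 5.4.2-2 and discussion with the Clinical Management Committee give partial cover, but none is a routine liver test.

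**Stronger readings a reader might infer are not supported.**

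- That a mandatory rule is unworkable: the text says *should*, and the rash and Grade 4 criteria do not depend on scheduled LFTs.
- That the gap reaches 326 to 382 days, by adding the 270-day entry window of Letter of Amendment #4 to 56 to 112 days: this requires that no Step 1 visit follow confirmation. Sections 3.0 and 6.2.6 suggest Step 1 visits may continue, which could place a week 28 LFT closer to entry.
- That an LFT at SVR12 is missing for the rule: 12 weeks after treatment it cannot inform a decision to stop.

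**Conclusion.** The concern holds in a limited form. If the original page confirms the LFT row, the ALT/AST and direct-bilirubin criteria have no scheduled measurement at 0 of 3 to 0 of 6 visits, over 56 to 112 days of G/P. They can be triggered only by an ad hoc, co-medication-prompted or failure-confirmation test. The reference value for Step 2 is also left unclear.

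The weight is modest. Step 2 is exploratory (objective 1.4.4), about 2 participants of 44 are expected to miss SVR12 under the design assumption of 95%, and about 9 at 80%. SVR12 is not affected. It is still worth correcting, because it concerns safety during the longer exposure and the correction is cheap. The conclusion assumes that the table was read correctly, that 8.1.1 applies in Step 2, and that the Manual of Procedures does not already add these tests.

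**What to change.** First check the LFT row of Table 6.1-2 against the original page and the Manual of Procedures. Then, in one letter of amendment:

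1. In Table 6.1-2, mark LFTs for participants receiving G/P at Step 2 entry, R+2 (ribavirin regimens), R+4, R+8, R+12, R+16 and premature treatment discontinuation. Hematology and chemistries are already drawn at all of these. For virtual visits, 6.3.21 already lets safety tests be done at a local commercial laboratory.
2. In 8.1.1, state whether the Step 1 or the Step 2 entry value is the reference in Step 2. This is the sponsor's choice. Where ALT has fallen since Step 1, the Step 2 value gives a lower threshold and more stops, and G/P stopped for toxicity is not resumed. The Step 1 value may set the threshold too high to protect. A minimum multiple of ULN is one way to limit needless stops.

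The cost is 3 (2A), 4 (12 weeks without ribavirin), 5 (2C) or 6 (2B) extra LFT panels per Step 2 participant on G/P, plus one at any premature discontinuation, and possibly a few more stops. If every expected non-SVR participant of 44 entered and took 2B, that would be 2.2 × 6 = 13.2 panels at 95% and 8.8 × 6 = 52.8 at 80%. No visit is added.

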4.1.2 Men and women age  $\geq 18$  years

4.1.3 A documented confirmation of acute HCV infection within 24 weeks prior to entry or HCV reinfection as described below:

Acute HCV infection will be defined as meeting one of the following criteria, depending on whether the participant was never previously infected or previously infected with clearance (treatment induced or natural) and after exclusion of other causes of acute hepatitis:

Never Previously Infected:

New (<24 weeks prior to Step 1 entry) ALT elevation to  $\geq 5$ X upper limit of normal (ULN) OR >250 U/L in participants with documented normal ALT in the preceding 52 weeks or  $\geq 10$  x ULN OR >500 U/L in participants with abnormal or no measured ALT baseline in the 52 weeks prior to study entry with detectable HCV RNA.

OR

Detectable HCV RNA with prior negative anti-HCV antibody (Ab) within 24 weeks prior to study entry or prior undetectable HCV RNA within 24 weeks prior to study entry.

Previously Infected:

For those with evidence of previous infection (as evidenced by positive anti-HCV Ab), documentation of clearance of prior infection either spontaneously with two negative HCV RNA a minimum of 12 weeks apart or after treatment with negative HCV RNA a minimum of 12 weeks after last dose of anti-HCV treatment AND meeting one of the following criteria in addition to exclusion of other causes of acute HCV:

New (<24 weeks prior to Step 1 entry) ALT elevation to  $\geq 5$  x ULN OR >250 U/L in participants with documented normal ALT in the preceding 52 weeks or  $\geq 10$  x ULN OR >500 U/L in participants with abnormal or no measured ALT baseline in the preceding 52 weeks with detectable HCV RNA.

OR

Detectable HCV RNA with prior undetectable HCV RNA within 24 weeks prior to study entry.

- 4.1.4 Detectable HCV RNA at the screening visit.
- 4.1.5 HCV genotype obtained within 24 weeks prior to entry by any US laboratory that has a Clinical Laboratory Improvement Amendments (CLIA) certification or its equivalent, or at any network-approved non-US laboratory that operates in accordance with Good Clinical Laboratory Practices (GCLP) and participates in appropriate external quality assurance programs.
- 4.1.6 HIV-1 infection status documented as either absent or present, as defined below:

For participants self-reporting as HIV-1 negative, HIV-1 infection testing should be performed at screening via rapid HIV-1 and/or enzyme or chemiluminescence immunoassay (E/CIA) test kit.

OR

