b) On a stable, protocol-defined compatible ART regimen (per [sections 2.2](#) [Rationale for Inclusion of Concomitant ART Regimens] and [5.4.1](#)) for >2 weeks prior to starting G/P with a CD4+ T-cell count >100 cells/mm $^3$  within 180 days prior to the screening visit. Laboratory testing can be done by any laboratory that has a CLIA certification or its equivalent or at any network-approved non-US laboratory that operates in accordance with GCLP and participates in appropriate external quality assurance programs.

4.1.9 The following laboratory values obtained within 28 days prior to study entry by any US laboratory that has a CLIA certification or its equivalent, or at any network-approved non-US laboratory that operates in accordance with GCLP and participates in appropriate external quality assurance programs.

- International normalized ratio (INR) <1.5  
NOTE: INR  $\geq 1.5 \times$  ULN is acceptable in participants with known hemophilia or stable on an anticoagulant regimen affecting INR, at the discretion of the site PI.
- Albumin  $\geq 3.0$  g/dL

4.1.10 Female participants of reproductive potential (defined as a person who has not been post-menopausal for at least 24 consecutive months, i.e., who has had menses within the preceding 24 months, or women who have not undergone surgical sterilization, specifically hysterectomy and/or bilateral oophorectomy or bilateral salpingectomy), must have a negative serum or urine pregnancy test within 48 hours prior to study entry by any US clinic or laboratory that has a CLIA certification or its equivalent, or is using a point-of-care (POC)/CLIA-waived test or at any network-approved non-US laboratory or clinic that operates in accordance with GCLP and participates in appropriate external quality assurance programs. The serum, urine, or POC pregnancy test must have a sensitivity of at least 25 mIU/mL.

4.1.11 All participants of reproductive potential must agree not to participate in a conception process (e.g., active attempt to become pregnant, in vitro fertilization) while on study treatment and for 6 weeks after stopping protocol-specified medication.

4.1.12 When participating in sexual activity that could lead to pregnancy, all participants of reproductive potential must agree to use at least one reliable form of contraception while receiving protocol-specified medication, and for 6 weeks after stopping the medication. Such methods include:

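### Section 8.1.1 can permanently end G/P on a direct bilirubin that is still normal, because the stop is a multiple of the entry value with no ULN floor (minor; a cheap improvement)

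*Protocol*

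**What the plan says.** Protocol section 8.1.1 lists four criteria under the instruction "Participants who meet any of the following laboratory criteria should stop treatment with G/P". Meeting any one is enough.

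- "Confirmed elevation of ALT and/or AST": more than three times the value at study entry.
- "Confirmed direct bilirubin": more than twice the value at study entry. This line does not use the word elevation.
- Rash: at least Grade 3, with constitutional symptoms.
- Any other event: Grade 4 and judged related to G/P.

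The last two carry a grade condition. The two liver lines carry no ULN multiple, grade, symptom or relatedness condition. The same section rules out dose reduction and adds: "If G/P is stopped for toxicity, it will not be restarted". Section 9.1 gives drug-related toxicity as a ground for discontinuation and refers back to 8.1, without adding a floor. None of the letters of amendment or clarification memos in the file changes 8.1 or 8.1.1.

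**The concern.** A multiple of entry is a sensible yardstick in acute HCV. One route in 4.1.3 requires ALT of at least 5×ULN or 10×ULN (or the U/L equivalents), so a fixed stop at 3×ULN could already be exceeded on day 0. The gap is at the other end. When the entry value is low, the multiple can fall inside the normal range, and nothing in the two liver lines prevents the stop from applying there.

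Low entry values are allowed. Section 4.1.3 also admits people on testing history alone, for example "Detectable HCV RNA with prior negative anti-HCV antibody (Ab) within 24 weeks prior to study entry", with no ALT requirement. The laboratory limits in 4.1.9 ("The following laboratory values obtained within 28 days prior to study entry by any US laboratory") cover only INR and albumin. No eligibility criterion sets a level for bilirubin.

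At stake is a participant's 4-week course, ended without possibility of restart on a value that the laboratory would report as normal. If the site records the stop as due to an AE, the participant also counts against the tolerability outcome in 10.2.1.3.

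**Working it through.** The plan states no figure on this point, so there is none to reproduce. The check is direct arithmetic.

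**Inputs**
- Multiples, both strictly exceeded and confirmed: 2 for direct bilirubin, 3 for ALT/AST (8.1.1).
- Direct bilirubin belongs to the LFT panel (6.3.8), drawn at entry and weeks 1, 2 and 4 (Table 6.1-1). Week 4 is treatment completion, so the scheduled draws that can cut the course short are weeks 1 and 2.
- Course length: 4 weeks, 28 days (5.1.1).
- Windows for weeks 1 and 2: ±3 days (6.2.3).
- Time to confirmation is not given for liver tests. Assumed: 0, 3 or 7 days.

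**Stop level.** Let e be entry value/ULN and m the multiple. The stop applies when confirmed value/ULN > m × e. A stop within the normal range is possible when m × e < 1, that is, e < 1/m.
- Direct bilirubin: e < 1/2 = 0.5.
- ALT/AST: e < 1/3 = 0.33.

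| Entry (×ULN) | Direct bilirubin stops above (×ULN) | ALT/AST stops above (×ULN) |
|---|---|---|
| 0.2 | 0.4 | 0.6 |
| 0.3 | 0.6 | 0.9 |
| 0.4 | 0.8 | 1.2 |
| 0.5 | 1.0 | 1.5 |
| 1.0 | 2.0 | 3.0 |

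**Effect of a ULN floor.** The stop level becomes the larger of m × e and 1. For direct bilirubin at entry 0.4×ULN it moves from 0.8 to 1.0×ULN. At entry 0.5×ULN or higher it does not move. For ALT/AST nothing moves once entry reaches 0.33×ULN.

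**How much of the course would have been taken.** Share = (visit day + confirmation days)/28.
- After week 1: 7/28 = 25%, 10/28 = 36%, 14/28 = 50%.
- After week 2: 14/28 = 50%, 17/28 = 61%, 21/28 = 75%.
- Using the visit windows, the extremes are (7 − 3 + 0)/28 = 4/28 = 14% and (14 + 3 + 7)/28 = 24/28 = 86%.

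**Consequence for the outcomes.** Section 10.1 keeps everyone who starts treatment in the primary analysis. Section 10.2.1.1 judges SVR12 on HCV RNA 12 weeks after treatment discontinuation. A participant stopped early is therefore still assessed and can still be a success.

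**Frequency.** The documents give no distribution of entry bilirubin, ALT or AST. Section 2.1 cites 0.1% of trial participants stopping G/P for adverse reactions over 8–16 weeks. The stopping rules of those trials are not shown, so this figure does not measure how often the present rule would be met.

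**The case against.** The best defence is context. The list sits under side effects of G/P, within a section on toxicity, and 7.1 describes an AE as something unfavorable, including an abnormal laboratory result. On that view a site would not treat a normal bilirubin as toxicity. That is how a sensible clinician might act, but the list does not say so: its trigger is the laboratory ratio alone, and a site following it literally would stop. Nor does confirmation help. It protects against one spurious result, but a repeat value of 0.9×ULN after entry at 0.4×ULN is both confirmed and normal.

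A second defence is that caution is reasonable here, since boosted darunavir and cobicistat regimens that raise glecaprevir exposure are allowed (2.2, 11.0). That stands as a reason to keep the entry multiple. It does not argue against a ULN floor, which leaves every stop at an above-normal value in place.

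The objection does succeed against several stronger readings that a reader might infer:

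- *ALT/AST is an equal problem.* It needs entry below 0.33×ULN in a viremic participant with acute HCV, which is close to theoretical.
- *Sections 8.1 and 8.1.1 contradict each other.* Section 8.1 says "Grades 1 and 2 AEs associated with G/P or RBV require no change in study treatment but close follow-up" and names only RBV anemia as an exception. But it also says "the principles in the following sections will be used to determine the appropriate dose adjustment", which supports 8.1.1 as governing. Whether a given rise would be Grade 1 or 2 depends on a grading table that is cited but not reproduced, so a conflict cannot be shown.
- *An early stop is an SVR12 failure, or a cure lost.* It is not itself a failure under 10.1 and 10.2.1.1, and cure at 4 weeks is the hypothesis under test (2.2 calls efficacy and duration in the acute phase unknown).
- *The participant loses Step 2.* Section 4.3.2 asks for completion of the Step 1 regimen, while 5.1.1 and 6.2.4 send those with recurrence or failure to Step 2. That is a separate question and carries no weight here.
- *The tolerability result is distorted.* That requires the stop to be recorded as due to an AE, which is doubtful for a normal value under 7.1.

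**Conclusion.** The point holds, chiefly for direct bilirubin. As written, 8.1.1 can permanently end G/P on a confirmed value within the normal range whenever entry is below 0.5×ULN. The thresholds of 0.5 and 0.33×ULN follow from the protocol's multiples and need no assumption. The course-share figures rest on assumed confirmation times. The number of participants affected cannot be estimated and is probably small. The documents do not support a claim that the primary analysis is compromised. Severity is minor: this is a cheap improvement to a stated rule.

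**What to change.** Amend the two liver criteria in 8.1.1 so that each applies only when the confirmed value exceeds the entry multiple and is also above ULN: direct bilirubin above twice entry and above ULN; ALT and/or AST above three times entry and above ULN. Any higher floor, such as Grade 3, is a clinical judgement for the team and is not needed to close this gap.

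As an optional clarification, 8.1 could name the 8.1.1 liver criteria as an exception to its Grade 1–2 sentence, as it already does for RBV anemia.

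The cost is one clause by letter of amendment (two with the optional one). No new test is needed, because the full LFT panel is already drawn at entry and on treatment. The downside is that a participant whose rise stays within the normal range is followed closely rather than stopped.
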